-4-day food record form to be explained and given to patient

-Bouchard activity questionnaire administered (bionutrition visit at the MGH CRC will be done at same time while patient is undergoing the urine collections for intestinal permeability study on the CRC)

4. Cognitive Function Instrument (CFI), and Patient's Assessment of Own Functioning Inventory (PAOFI) Questionnaire.

For HIV-Negative Control Participants in Neurological Substudy only:

Visit A (Screen Visit):

- 1. Participant will meet with study investigator to review the consent form and signing of informed consent
- 2. Detailed medical history, including assessment of history of anti-retroviral use, hepatitis status, nadir CD4 count, gastrointestinal disease, prior history of CNS opportunistic infections and risk factors for cardiovascular disease, including smoking history, family history, and history of recreational drug use
- 3. Physical examination

- 4. Fasting blood will be obtained for glucose, comprehensive metabolic panel, amylase (only for subjects who are enrolled in the randomized study), lipase (only for subjects who are enrolled in the randomized study), creatinine, insulin, hemoglobin A1c, Prothrombin Time / INR, Partial thromboplastin time (PTT), CBC plus differential, lipids, high-sensitivity C-reactive protein, T-cell subset, and HIV RNA (for HIV-infected patients) and HIV ELISA test (for HIV-negative controls). Additional blood will be collected for isolation of peripheral blood mononuclear cells for immunological studies (60 mL of blood), serum and plasma to be frozen and stored.
- 5. Urine HCG for women.
- 6. Food diary and nutrition.
- 7. Cross-sectional computed tomography (CT) scan: non-contrast enhanced 1cm cross-sectional CT scan of the abdomen to determine visceral adipose tissue (VAT) area and abdominal subcutaneous adipose tissue (SAT) area.
- 8. Cardiac CTA. Subjects who have had a cardiac CTA less than 3 months prior to visit A will not have a cardiac CTA at visit A.

Visit B:

- 1. Serum HCG will be obtained STAT as a pregnancy test for women prior to FDG-PET
- 2. Blood drawing for RNA-sequencing, and for sera and plasma to be frozen for assays to be run in batch using kits.
- 3. Food diary will be collected from Visit A 4. FDG-PET/CT
- 5. Neurocognitive Test Battery administered between 18F-FDG tracer injection and prior to FDG PET/CT scan.
- 6. Center for Epidemiological Studies-Depression Scale (CES-D).
- 7. Cognitive Function Instrument (CFI), and Patient's Assessment of Own Functioning Inventory (PAOFI) Questionnaire.

Data Collection/Study Procedures:

Multidetector Cardiac CT and CT Coronary Angiography (CCTA): Image acquisition will take place at MGH using the "SOMATOM Definition Flash", a second generation dual source 128 detector-row CT scanner (Siemens Medical Solutions, Forchheim, Germany). Based on a 280 millisecond gantry rotation speed this allows for a temporal resolution of 75 milliseconds, independent of heart rate. The study protocol employs several state-of-the-art technologies to minimize radiation dose. Semiautomated reference tube current selection and exposure control (CAREDose 4D, Siemens AG) are tailored to the subject's body size, in conjunction with semiautomated reference tube potential (voltage) selection (CARE kV, Siemens, AG), with individually adapted exposure settings on a per-patient basis. Prospective ECG-triggered axial-sequential or retrospective ECG-gated spiral with adaptive pulsing scan modes are used based on the heart rate and rhythm. Iterative image reconstruction algorithms allow for further reductions in radiation dose. These techniques allow for an up to 50% reduction in radiation dose compared with previous generation protocols.

The study protocol is based on the standard clinical CCTA protocol at MGH. Intravenous access will be obtained, most commonly in the right antecubital vein. The subject's blood pressure will be taken, and ECG leads will be attached to monitor heart rate and rhythm. At the supervising physician's discretion, for heart rates over 65 beats per minute or with significant variability, an intravenous dose of 5 mg metoprolol tartrate will be administered, and repeated once if insufficiently effective. Sublingual nitroglycerin (0.6 mg) will also be administered as per standard protocol for cardiac CT scans. Contraindications to metoprolol include hypotension (systolic blood pressure < 90 mm Hg), active asthma requiring inhalers on the day of scan, first degree heart block, or narrow-angle glaucoma. Contraindications to nitroglycerin include hypotension, severe aortic stenosis, or phosphodiesterase type 5 inhibitor (e.g. sildenafil, tadalafil, vardenafil) use within the preceding 5 days. A prospectively-ECG triggered noncontrast CT of the heart is obtained to measure coronary and aortic calcium. The test bolus

method will be used to plan the CTA timing, via a test bolus injection of contrast medium (20 ml), followed by a saline flush (40 ml). Contrast-enhanced CT acquisition: the contrast bolus is injected: 60-100 ml of nonionic iodinated contrast based on subject size (iopamidol 370 g/cm³, Isovue 370, Bracco Diagnostics, Princeton, NJ), followed by a flush of 40 ml of saline. After a delay based on the test bolus, a CT acquisition is performed from the carina to the diaphragm: tube voltage 80 - 120 kVp, tube current-time product reference 320 mAs, detector collimation 2 x 128 x 0.6 mm. A number of high-resolution images of the heart at slightly different time-positions within the cardiac cycle will be reconstructed, of which the best phase will be used to evaluate the coronary artery lumen, plaque distribution and morphology.

18-FDG PET/CT: An approach to detecting macrophage activity in atherosclerotic plaques uses FDG as the contrast radiotracer for positron emission tomography (PET). FDG competes with glucose for uptake into metabolically active cells, including macrophages in atherosclerotic plaques, and is trapped inside cells after phosphorylation. FDG-PET can image metabolic activity (as a marker of plaque inflammation) quantitatively in atherosclerotic plaques^{43,44}, has been shown to have high reproducibility⁴⁵, and correlates with histologic data⁴⁴. Taking advantage of the myocardium's preference for free fatty acids over glucose as an energy source, to minimize myocardial glucose uptake in order to better visualize coronary plaque activity, patients will be asked to adhere to an Atkins style diet for the evening prior to imaging and then to fast overnight. Cardiac PET/CT imaging will be performed two hours following intravenous administration of approximately 10mCi of 18-FDG. Imaging will be performed using a Siemens Biograph PET/CT system (Siemens Medical Solutions, Forchheim, Germany) Once co-registered, the standardized uptake value (SUV) of FDG will be measured in various arteries. The SUV is the decay-corrected tissue concentration of FDG (in kBq/ml) divided by the injected dose per body weight (kBq/g). Target-to-background ratio (TBR) will be calculated for each vascular segment as the segment SUV divided by vena cava or atrial blood SUV. FDG uptake in the brain will also be assessed.

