Among patients living with HIV infection, cardiovascular disease (CVD) is increasingly prevalent and has become a significant cause of mortality. Identifying the mechanisms that are distinctive to the atherosclerotic disease process in HIV-infected patients is crucial to develop appropriate strategies to treat and prevent CVD in this patient population. Activation of the innate immune system may stimulate inflammatory mechanisms of atherosclerosis development. Loss of gastrointestinal (GI) mucosal epithelial integrity and loss of CD4+ T-lymphocytes in the intestinal lamina propria occur in HIV-infected patients. Translocation of microbial products from the intestinal lumen into the systemic circulation has been demonstrated to be increased in HIV-infected patients and we hypothesize to be a key driver of monocyte and macrophage activation. In turn, these pro-inflammatory monocytes and macrophages can induce atherosclerotic disease development. However, the respective roles of microbial translocation and the gut mucosal immunity on cardiovascular inflammation in HIV infection are not yet known. Furthermore, no treatment strategy as yet exists to effectively target proatherogenic immune activation as an important mechanism of CVD in HIV-infected patients.

Our central hypothesis is that increased microbial translocation from impaired epithelial integrity and impaired mucosal immunity activates the innate immune system, causing proatherogenic monocyte and macrophage activation and atherosclerotic disease development in HIV disease. Furthermore, we hypothesize that intervening to enhance the intestinal epithelial barrier using a glucagon-like peptide 2 (GLP-2) analog will decrease intestinal permeability to microbial products and thus ameliorate monocyte/macrophage pathways that lead to downstream decrease in arterial macrophage activity, inflammation and atherosclerotic disease risk. *We will test our hypotheses in studies proposed in the following specific aims:*

Aim 1: To determine the role of innate immune system activation in atherosclerosis development among HIV-infected patients, focusing on microbial translocation from impaired GI mucosal barrier as the hypothesized inciting event for activation of monocytes and macrophages.

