A) To determine how intestinal epithelial integrity (assessed via characterization of intestinal tissue tight junctions and also via GI permeability probe studies) and microbial translocation relate to measures of monocyte and macrophage activation and to measures of CVD risk utilizing functional imaging (by ¹⁸fluorodeoxyglucose positron emission tomography (FDG-PET) and structural (cardiac CTA) cardiac imaging to assess arterial inflammation and coronary atherosclerotic disease.

B) Trancriptome analysis of circulating monocytes using RNA-Seq to identify distinctive genomic signatures in monocytes of HIV-infected patients with greatest amount of coronary atherosclerosis detected on CTA compared to HIV-infected patients without atherosclerosis to elucidate novel biological pathways involved in atherogenesis in HIV disease. These pathways will also be compared to dysregulated pathways in HIV patients with greatest degree of intestinal permeability/microbial translocation compared to patients with the least. We hypothesize that biological pathways in monocytes stimulated by microbial translocation will be similar to pathways activated in monocytes of patients with greatest degree of CVD.

Aim 2: Determine the effects of a glucagon-like peptide-2 analog, teduglutide, on intestinal epithelial integrity, on microbial translocation across the gut lumen, on markers of innate immune system activation including the monocyte transcriptome, and on arterial inflammation in a 6-month randomized, double-blind placebo-controlled proof of concept trial in HIV-infected individuals.

Exploratory Aim: An additional exploratory aim is to study the interrelationships between cerebral glucose metabolism measured by FDG-PET of the brain (a proxy for neural activity), cognitive performance and arterial inflammation as well as gut microbial translocation in patients living with HIV.

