[name] of the MGH Biostatistics Center has provided biostatistical consultation regarding power calculations and design for the proposed studies. [name] biostatistical support will continue to be readily available for randomization, data analysis, and manuscript preparation.

Statistical Analysis Plan:

Baseline Study Part 1: Biomarkers, Immunology and Intestinal Permeability Studies and **Baseline Study Part 2: Colonoscopy, Cardiac CTA and FDG-PET/CT Studies (Aim 1A):** The statistical approach to assess correlations between intestinal permeability and microbial translocation with innate immune activation and cardiovascular disease. For mechanistic modeling, we will perform bivariate exploratory analysis followed by multivariate linear regression models to explain the impact of microbial translocation on cardiovascular inflammation.

Univariate analysis: To identify relationships between GI epithelial integrity, markers of innate immune activation and markers of microbial translocation with cardiovascular markers of vascular inflammation (TBR measured by FDG-PET) and atherosclerosis (segments with plaque) in HIV-infected patients, we plan to use linear correlation coefficients for continuous predictor variables (Pearson correlation coefficients if variables are normally distributed or Spearman correlation coefficients if their distributions are non-normal) to assess bivariate relationships between cardiovascular imaging measurements and measured covariates hypothesized to be associated with atherosclerosis development and vascular inflammation.

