*Multivariate modeling:* For outcomes TBR and plaque, to control for potential confounders, multivariate linear regression modeling will be used to identify factors independently associated with increasing TBR and increasing number of atherosclerotic plaque lesions. Similar methods will be applied for neurocognitive score and mood assessment to cerebral FDG-PET/CT. Model variable selection will be based on "change-in-estimate" method⁵⁸. Candidate covariates to be chosen for entry into our model include all covariates significant on individual univariate models (p<0.05), potential confounders, and biologically plausible covariates with established relationships to atherosclerosis. Colinearity among covariates will be identified and redundant covariates will be excluded from the model. Confounders will be identified by observing changes in effect estimate β ; colinearity will be identified by observing changes in effect estimate β ; as well as by using Variance Inflation Factor criterion. Regression diagnostics will be used to check if model assumptions are met⁵⁸. We will control for age, gender, race, smoking, lipids, diabetes mellitus, WRAT 4 reading versus educational years, and hypertension in addition to other potential confounders identified by methods above.

Between group comparisons: We will also assess differences in microbial translocation, mucosal immunity and GI permeability markers among those with coronary atherosclerosis vs. those without atherosclerosis and in those with elevated TBR (>1.8) vs. those without elevated TBR. 2 group comparisons will be performed using Student's T-test if the outcome variable is normally distributed. Distributions will be tested for normality using the Wilk-Shapiro test and examination of the histogram distributions. If the outcome variable is not normally distributed, we will consider appropriate transformation to approximate a normal distribution. Alternatively, if distributions are non-normal despite the applied transformation, we will use nonparametric Wilcoxon rank sum test to compare the 2 groups. All tests will be 2-sided, and a p < 0.05 will be considered statistically significant.

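### Aim 1A asks how gut integrity and translocation relate to monocyte/macrophage activation, but the plan gives that link only a correlation and names no activation marker as an outcome of its adjusted models.

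*Combined protocol and SAP*

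**What the plan says.** Section II (Specific Aims) describes Aim 1 as "focusing on microbial translocation from impaired GI mucosal barrier as the hypothesized inciting event for activation of monocytes and macrophages". Aim 1A then sets two questions side by side: how intestinal integrity and "microbial translocation relate to measures of monocyte and macrophage activation and to measures of CVD risk". The Research Design text for Aim 1A repeats both.

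The statistical analysis plan for Baseline Study Parts 1 and 2 (Aim 1A) treats the two questions differently:

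- Its opening sentence says the approach is to "assess correlations between intestinal permeability and microbial translocation with innate immune activation and cardiovascular disease". This is the only place where an Aim 1A analysis of translocation against innate activation is named.
- The next sentence gives the purpose of the modelling: "multivariate linear regression models to explain the impact of microbial translocation on cardiovascular inflammation".
- The univariate paragraph describes pairs made of a cardiovascular imaging measure and a covariate.
- The multivariate paragraph begins "For outcomes TBR and plaque, to control for potential confounders, multivariate linear regression modeling will be used" and adds "Similar methods will be applied for neurocognitive score and mood assessment to cerebral FDG-PET/CT". It lists age, gender, race, smoking, lipids, diabetes, WRAT 4 reading versus educational years, and hypertension as covariates to control for, plus other confounders found by change-in-estimate.
- The between-group comparisons are unadjusted and split participants by plaque or by TBR.

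**The concern.** The second question of Aim 1A (translocation and imaging) gets a bivariate step followed by an adjusted model. The first (translocation and monocyte/macrophage activation) gets only the bivariate step. The plan considers age, smoking, lipids, diabetes and the rest worth controlling for in its regressions, and gives no reason why they would matter less when the outcome is sCD163 or MCP-1.

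Anything that raises both LPS or permeability and an activation marker would produce a correlation with no direct link behind it. Followed as written, the plan has no prespecified way to tell the two apart in the cross-sectional data.

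**Working it through.** **1. Is there an adjusted model for this link anywhere?**

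| Component | Outcome | Confounder control | Estimates translocation vs activation in the 70? |
|---|---|---|---|
| Aim 1A, opening sentence | innate activation and cardiovascular disease | none stated | yes, unadjusted |
| Aim 1A, univariate | imaging measures | none | no |
| Aim 1A, multivariate | TBR, plaque; neurocognitive score and mood against cerebral FDG | yes | no |
| Aim 1A, between groups | gut and translocation markers by plaque or TBR status | none | no |
| Aim 1B | monocyte transcriptome, 7 highest vs 7 lowest translocation | matching; active smokers excluded | no: 14 selected patients, not the plasma markers |
| Aim 2 | change in each marker by arm | randomisation; adjusted mixed model | no: estimates the treatment effect on each marker |

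Activation markers may enter the TBR and plaque models as covariates, but there they help to explain imaging. They are not the response.

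**2. The plan's own detectable correlation.** The inputs are n = 70, two-sided 5% and 80% power (Sample Size Determination, Aim 1A). By Fisher's z, with 1.96 + 0.84 = 2.80:

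- r = tanh(2.80/√(70 − 3)) = tanh(2.80/√67) = 0.330. The plan's 0.33 is reproduced, and it is an unadjusted figure.

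**3. Cost of adjusting.** With k covariates, r = tanh(2.80/√(n − k − 3)). The plan names 8 covariates, or 7 without WRAT 4. I assume one degree of freedom each.

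- n = 70, k = 7: tanh(2.80/√60) = 0.347
- n = 70, k = 8: tanh(2.80/√59) = 0.349
- n = 70, k = 10 (the 7 plus three HIV variables): tanh(2.80/√57) = 0.355
- n = 60, k = 8 (biopsy-based exposures): tanh(2.80/√49) = 0.380
- k = 15, as an upper case: 0.37 at n = 70 and 0.41 at n = 60

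Power at r = 0.33 with n = 70 falls from 80% to 75% (k = 8) or 70% (k = 15).

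**4. What confounding could do (assumption).** The documents give no correlation of any covariate with LPS, permeability, sCD163 or MCP-1. Suppose one confounder has correlation c with both markers and there is no direct link. The marginal correlation is then c². The chance that the unadjusted test is significant at n = 70 is Φ(atanh(c²)·√67 − 1.96) + Φ(−atanh(c²)·√67 − 1.96).

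| c | induced r = c² | probability of p < 0.05 |
|---|---|---|
| 0.2 | 0.04 | 6.2% |
| 0.3 | 0.09 | 11.4% |
| 0.4 | 0.16 | 26.2% |

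**5. Are the data there?** LPS, sCD163 and MCP-1 are planned for all 70 HIV-infected participants. The sugar-probe test is in Visit 2 of both the full and the Part 1-only schedules. T-cell subsets, nadir CD4 and hepatitis status are collected at Visit 1 of both. WRAT 4 is not in the Part 1-only schedule. Biopsies exist for 60 HIV-infected participants.

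**The case against.** The strongest reply is that the plan can be read more generously. The opening sentence covers innate activation, the next describes mechanistic modelling by bivariate analysis and then regression, and the sentence listing the covariates is not itself tied to TBR or plaque. That is fair as to intent. It does not fill the gap, because wherever the text names what the regressions are for, it names cardiovascular inflammation, TBR, plaque or the neurological outcomes.

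A reader might infer that the central hypothesis would be judged on an unadjusted correlation alone. The documents do not support that. The protocol introduces the randomised trial as a further test of the hypothesis; Aim 2 compares activation and translocation markers between arms and adds an adjusted mixed model; and Aim 1B is matched. These are other evidence on the hypothesis. What they leave open is the Aim 1A association itself.

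A reader might also infer a large false-positive rate. Higher figures than those above need several confounders all acting in the same direction. Opposing confounders could cancel, and a single weak one (c = 0.2) barely moves the error rate. Adjustment restores 5% only if the confounders that matter are measured and in the model. A list built around cardiovascular risk may miss HIV-specific ones. Both objections stand, and the second shapes the fix.

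Finally, a reader might extend the point to the exploratory aim on brain FDG and cognition. That aim promises only to study interrelationships, the similar methods could admit TBR and LPS as candidate covariates, and mood is not named in it. I do not press it.

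A short stretch of text just before the statistical section was not available to me. If it specifies an adjusted model for activation markers, the point falls.

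**Conclusion.** The point holds as a gap in Aim 1A. One of its two stated questions has no prespecified confounder-adjusted analysis, although the covariates are named and the data are planned. The trial's primary outcome and the plan's detectable correlations are unaffected.

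The direction and size of any bias are unknown from the documents. The 6% to 26% range is illustrative and rests on one confounder, equal correlations of 0.2 to 0.4 with both markers, and no true link. The cost of adjusting is firmer: it depends on the planned n and on the number of covariates, with one degree of freedom each assumed.

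**What to change.** In the Multivariate modeling paragraph for Aim 1A, make the list of outcomes TBR, plaque, sCD163 and MCP-1, and specify the two new models:

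- **Population:** the 70 HIV-infected participants.
- **Exposures:** plasma LPS and the sugar-probe permeability measure. Do not use sCD14 on either side, because the protocol lists it both as a translocation marker and as an activation marker.
- **Covariates:** those already listed, without WRAT 4, which Part 1-only participants do not have.
- **Candidate confounders:** HIV variables already collected, such as CD4 count, nadir CD4 and hepatitis status.
- **Reporting:** base the Aim 1A statement on translocation and activation on the adjusted coefficient, and show the unadjusted correlation beside it.

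The cost is a change of wording and a few regressions on planned data. The detectable correlation at 80% power rises from 0.33 to about 0.35 with 7 or 8 covariates (0.355 with 10). If biopsy-based integrity is also used as an exposure, it is about 0.38 in the 60 participants with biopsies. Two exposures and two outcomes give 2 × 2 = 4 coefficients; all four should be reported with confidence intervals.
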